### State your secondary study objectives

**Aim 2:** Examine the impact of PainPac on pain severity, pain interference, pain self-efficacy, emotional distress, and quality of life (secondary outcomes for secondary aim).

**Hypothesis:** PainPac will demonstrate improvements in pain-related outcomes (e.g., self-efficacy, emotional distress) and quality of life for patients that are at least equivalent to the improvements experienced by PCST-Video participants.

**Aim 3:** Gather quantitative and qualitative post-treatment data on patients' preferences, confidence in using technology, barriers, and facilitators regarding PainPac to update and optimize PainPac for a future large randomized clinical effectiveness trial.

**Hypothesis:** This data will lead to optimization of PainPac to improve pain-related outcomes in cancer patients.

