## Design & Procedures

- Describe the study, providing details regarding the study intervention (drug, device, physical procedures, manipulation of the subject or the subject's environment, etc.). Discuss justifications for placebo control, discontinuation or delay of standard therapies, and washout periods if applicable. Identify procedures, tests and interventions performed exclusively for research purposes or more frequently than standard of care. Include alternative therapies, concurrent therapies discontinued per protocol, risk benefit ratio, and use of tissue/specimens. Discuss monitoring during washout periods if applicable. Include brief description of follow-up, if any.

**Research Plan and Design.** We will use a pilot RCT to examine PainPac feasibility (primary aim and outcome), patient burden, engagement, acceptability, and initial pain-related outcomes, compared to a therapist led videoconference delivered behavioral pain intervention (PCST-Video) in colorectal cancer patients with pain (N=60). We will use quantitative and qualitative data to optimize PainPac. Participants will complete assessments at pre-treatment (A1), post-treatment (A2; 4 weeks post-A1), and 1 month follow-up (A3; 1 month post-A2) (months 5-22). Assessment contents can be found in the attached document, Data Dictionary, and will be distributed to both study groups. These assessments contain items that will be used to assess Aim 2 for both study groups. The pain management strategies are relevant and efficacious across cancer types. Due to the pilot nature of this work, we will enroll an opportunity sample of colorectal cancer patients. [name] (PI) has tested behavioral symptom management protocols in colorectal cancer patients and has an established relationship with [name] (Co-I) and the GI cancer clinic teams, all of which allows for an efficient start up. Further, colorectal cancer is associated with significant pain, impacts men and women, and spans a large age range, making it a good population for this early work. The preliminary work for PainPac has been in cancer patients including breast, prostate, lung, and stem cell transplant patients. If PainPac is feasible and shows promise, this project will lead to effectiveness testing in diverse cancer patients.

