**Randomization.** Following consent and baseline assessment, patients will be randomized with equal allocation to: 1) a mobile app behavioral cancer pain intervention (PainPac) or 2) a therapist led videoconference delivered behavioral cancer pain intervention (PCST-Video). For patients randomized to PainPac, eligibility will result in electronic push of study information to the patient through MyChart, email, and/or text, and research staff will confirm app download. All participants will continue to receive standard care from their medical team. No participant will be asked to change pain management strategies. Data from 2021 suggests the majority of Americans (85%) own a smartphone, and similar statistics are reported in cancer patients. Participants who do not have a smartphone will be loaned one with a data plan to access the PainPac app or PCST-Video sessions. Participants will receive instructions for PainPac or PCST-Video technology, handouts with FAQs and troubleshooting strategies, and contact information for the study team and tech support. Therapists and staff will check in with participants regarding technology usability and tech assistance will be available within 24 hours.

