
**Videoconference Delivered Pain Coping Skills Training (PCST-Video).** Participants randomized to PCST- Video will receive 4 behavioral cancer pain intervention sessions delivered by videoconferencing by

a pain therapist in the medical center to the patient in their natural environment (e.g., home). Sessions will be scheduled weekly for 45-60 min and mimic in person sessions. In rare circumstances when the participant is not able to connect via videoconferencing, the PCST-Video sessions can be delivered via phone. This is a backup option that will rarely if ever be used due to extenuating circumstances. PCST-Video session content is based on Pain Coping Skills Training (PCST) designed by [name] (mentor to Drs. [name] and [name]) and matches the PainPac skills modules described above. PCST-Video participants will complete assessments at the same intervals as PainPac participants. Interventionist Training (months 2-4). PCST-Video will be delivered by a masters or doctoral level psychologist with experience delivering behavioral pain interventions. Drs. [name] and [name] will provide training and therapists will be certified (>90% ratings of competence and protocol adherence) to deliver the intervention. Therapists will follow a manualized protocol; treatment strategies will be taught through didactic instruction, audio-/video-recorded illustration from model cases, and role-play of common scenarios. Sessions will be recorded and reviewed in supervision by [name]. Procedures to Ensure Consistency of Treatment. 1) The therapist will follow a manual; 2) Weekly supervision will occur; 3) Session recordings will be reviewed and feedback provided; and 4) Ratings of treatment adherence and competence will be conducted. Treatment Adherence and Therapist Competence. Ratings of protocol adherence will be made by Drs. [name] and [name]. Protocol adherence criteria will be developed for each session with satisfactory adherence ≥90% on the rating scale. Ratings of therapists' competence will be used to evaluate 20% of PCST-Video sessions.

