
number of times per week they practice the coping skills.  $\geq 3$  times/week will serve as the benchmark; if participants log into PainPac and/or practice the coping skills  $< 3$  times/week, PainPac will not be considered engaging. We expect engagement in PainPac will be at least comparable to PCST-Video. Acceptability will be indicated by 80% of patients reporting satisfaction with PainPac and PCST-Video ( $M=3.2/4$ ) on the CSQ. Aim 2. Between-group differences at follow-up will be characterized using Cohen's  $d$  and 95% confidence intervals. Consistent with recommendations for small pilot RCTs of behavioral interventions, we propose a conservative approach that focuses on describing effect size estimates and their variability instead of testing for significant group differences. As this is a small trial intended to provide signals the intervention is promising and data for a larger trial, all pre- to post-intervention and 1 month variables will be characterized using graphs/plots and descriptive statistics (e.g., mean, standard deviations, range). We will examine the pattern of findings to determine the best analytic plan for the subsequent trial. Pain may vary based on pain medications and disease stage/treatment; we will describe these variables and include them, when appropriate, as covariates in future larger trials. The subsequent trial will be fully powered to test two active conditions. Given our proposed sample size ( $N=60$ ), an a priori power calculation using G-Power suggests we will have  $>80\%$  power to detect medium-sized effects of  $d=0.74$  ( $\alpha=0.05$ , two-tailed). However, as noted above, our analytic plan focuses on describing between-group differences rather than testing for significant effects. Aim 3. We will use methods from applied thematic analysis to analyze interview data. First, we will create a codebook a priori that corresponds to major content areas from the interview guide. The codebook will include a coding matrix with categories, codes, and definitions. The analysts ([name] and a study member) will segment interview transcripts into major content areas using Nvivo and then use an inductive and iterative approach to identify data-driven codes. As new codes emerge, they will be applied to previously coded sections until all relevant information is captured. All codes will be grouped into themes and subthemes. The analysts will meet to discuss coding and resolve discrepancies in interpretation, and maintain an audit trail of coding and analytic decisions. The study team will review the qualitative findings and develop action steps for modifying the protocol. All data will be used to optimize PainPac for a large randomized clinical effectiveness trial. We will optimize areas related to patient preferences, barriers, beliefs, and cultural tailoring to increase usability and engagement and meet user needs.

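### Aim 2 names no baseline-adjusted group difference, although every outcome is measured in both arms before randomisation, so precision already paid for goes unused

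*Combined protocol and SAP*

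**What the plan says.** All Aim 2 analysis is in the Data Analysis & Statistical Considerations section. The between-group contrast is given in one sentence: "Between-group differences at follow-up will be characterized using Cohen's" d and 95% confidence intervals. The reason follows: "we propose a conservative approach that focuses on describing effect size estimates and their variability instead of testing for significant group differences".

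The baseline scores appear only in the descriptive output, where "all pre- to post-intervention and 1 month variables will be characterized using graphs/plots and descriptive statistics". Pain medication and disease stage or treatment are to be described now, with a plan to "include them, when appropriate, as covariates in future larger trials". The baseline outcome score is not mentioned as a covariate, now or later. No ANCOVA, change-score contrast or repeated-measures model is named anywhere in the document.

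The Design & Procedures section shows that the baseline is available. "Participants will complete assessments at pre-treatment (A1), post-treatment (A2; 4 weeks post-A1"), with A3 one month after A2. PCST-Video "participants will complete assessments at the same intervals as PainPac participants". On timing: "Following consent and baseline assessment, patients will be randomized with equal allocation to" the two arms. The Aim 2 hypothesis concerns change: PainPac's improvements are expected to be "at least equivalent to the improvements experienced by PCST-Video participants".

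**The concern.** A score measured before randomisation is a legitimate covariate. Where it correlates with the same score at follow-up, adjusting for it removes part of the between-patient variation from the group difference and narrows the interval. The section makes the effect size and its variability the Aim 2 deliverable, yet the one contrast it names leaves the baseline out.

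Three things are at stake:

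- **Width of the interval.** With 30 per arm it is already about one SD from end to end.
- **Chance imbalance.** No stratification is described. At 30 per arm the chance difference between arms in A1 has a standard error of √(2/30) = 0.26 SD, so for any one outcome it exceeds 0.25 SD in about one trial in three. Adjustment accounts for this; a follow-up-only d does not.
- **Planning the next trial.** The A1-to-follow-up correlation is needed to size a baseline-adjusted larger trial, and it is not among the statistics listed.

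The hypothesis is about improvement, and an adjusted difference speaks to that more directly than a raw follow-up contrast.

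**Working it through.** **Inputs from the plan.** N = 60, 30 per arm, equal allocation; attrition up to 25%, which leaves 0.75 × 60 = 45, taken as 23 and 22; d = 0.74, two-sided α = 0.05, power above 80%.

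**Assumption.** The A1-to-follow-up correlation r is not in the documents. It is shown at 0.3, 0.5 and 0.7.

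**The plan's own figure.** For a two-sample t-test, the noncentrality is 0.74 × √(30 × 30/60) = 2.87 on 58 degrees of freedom. Power is 80.5%, and the effect detectable with 80% power is 0.736. The stated figure reproduces. It is for an unadjusted comparison with all 60 analysed.

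**Half-width of the 95% interval**, in follow-up SD units, for d near zero:

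- Unadjusted: t(N−2) × √(1/n₁ + 1/n₂)
- ANCOVA on A1: t(N−3) × √[(1/n₁ + 1/n₂)(1 − r²)(1 + 1/(N−4))]
- Change score, equal SDs at A1 and follow-up: t(N−2) × √[(1/n₁ + 1/n₂) × 2(1 − r)]

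At 30/30, unadjusted: 2.002 × √(2/30) = 2.002 × 0.258 = 0.517. ANCOVA at r = 0.5: 2.002 × √(0.0667 × 0.75 × 1.0179) = 2.002 × 0.2256 = 0.452.

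| | r = 0 | r = 0.3 | r = 0.5 | r = 0.7 |
|---|---|---|---|---|
| 30/30 unadjusted | 0.517 | 0.517 | 0.517 | 0.517 |
| 30/30 ANCOVA | 0.522 (+0.9%) | 0.498 (−3.7%) | 0.452 (−12.6%) | 0.373 (−27.9%) |
| 30/30 change score | – | 0.612 (+18%) | 0.517 (0%) | 0.400 (−23%) |
| 23/22 unadjusted | 0.601 | 0.601 | 0.601 | 0.601 |
| 23/22 ANCOVA | 0.609 (+1.3%) | 0.581 (−3.4%) | 0.528 (−12.3%) | 0.435 (−27.7%) |

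ANCOVA breaks even at r = 0.14 (30/30) or 0.16 (23/22). An unadjusted trial would need about 32, 39 or 57 per arm to match the 30/30 ANCOVA widths at r = 0.3, 0.5 and 0.7. A simulation of 20,000 trials per setting gave the same half-widths to within 0.001, with coverage between 94.7% and 95.4% for both methods.

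**Pain severity.** Patients need pain of at least 4 at a clinic visit, and pain is re-assessed at enrolment. This can restrict the range of A1 and lower r. Simulations assumed 0–10 scores with mean 4 to 6 and SD 2 to 2.5, and a screening-to-A1 correlation of 0.6 to 0.8. The table shows the correlation left after selection and the 30/30 gain.

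| Selection assumed | r = 0.3 | r = 0.5 | r = 0.7 |
|---|---|---|---|
| One screening score, linked to follow-up only through A1 | 0.23–0.28 (2–3%) | 0.40–0.46 (8–11%) | 0.59–0.66 (19–24%) |
| Two separate scores, each at least 4, linked only through A1 | 0.21–0.27 (1–3%) | 0.37–0.45 (6–10%) | 0.56–0.65 (16–23%) |

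If one screening score also predicts follow-up as strongly as A1 does, r = 0.5 becomes 0.35–0.44, a gain of 5–9%. The other Aim 2 outcomes have no stated entry threshold.

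**The case against.** The strongest reply is that nothing the trial will decide depends on this. Aim 2 is secondary, the sample size rests on feasibility, and the section disclaims significance testing. The unadjusted d is unbiased with a valid interval, and no benchmark uses it. All of that stands, and it limits the weight of the point. It does not remove it: where estimates and their variability are the product, the width of the interval is a quality of the product.

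Four narrower objections have some force:

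- **The score entering d is not stated.** Raw follow-up values are the natural reading, but a d on change is not excluded. That reading would not rescue precision. With equal SDs, a change-score interval is wider than the follow-up-only one at r = 0.3, equal at 0.5, and still wider than ANCOVA at 0.7.
- **The list of descriptive statistics is illustrative.** The correlation could be computed later from the collected data. True, but committing to it costs one line. The deferred covariates are medication and disease variables, so that sentence is not a decision against baseline adjustment.
- **The gain is assumed.** At r = 0.3 it is slight. The imbalance still favours adjusting: about 1% lost at r = 0, up to 28% gained at r = 0.7.
- **Selection on two pain scores lowers the pain-severity range a little.** This is accepted and shown in the working.

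**Conclusion.** The point holds. The plan names no baseline-adjusted contrast for Aim 2, and the baseline is collected in both arms before allocation. The cost is avoidable imprecision, not bias or invalidity. For r from 0.3 to 0.7, adjustment would narrow the 95% interval by 4% to 28% at 30 per arm, and by 3% to 28% after 25% attrition. The gain for pain severity is probably smaller: across the selection scenarios it is 5% to 11% when r would be 0.5 without selection. These figures rest on assumed correlations, a linear relation to baseline and d near zero. The change should be made, but the plan would stand without it.

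**What to change.** Add to Aim 2 wording such as:

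> For each Aim 2 outcome, the lead between-group estimate at A2 and at A3 is the difference adjusted for the A1 score by ANCOVA, in raw units with a 95% confidence interval. If standardised, it is divided by the pooled unadjusted follow-up SD at that visit. Unadjusted Cohen's d on the follow-up score is kept as a description. The A1-to-A2 and A1-to-A3 correlations are reported for planning. The number analysed is given for each estimate. No significance tests are added.

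Dividing by the unadjusted SD keeps the adjustment itself from inflating d. Naming the lead estimate in advance prevents a later choice between the two. A change-score d should not be used instead, for the reason shown in the table.

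The cost is SAP wording and a few lines of code. ANCOVA uses about one degree of freedom per outcome. If r is near zero the interval is about 1% wider (0.9% at 30/30, 1.3% at 23/22). No new data or participants are needed.

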**Statistical Design and Analyses.** A pilot trial (N=60) will be used to compare PainPac (n=30) to PCST-Video (n=30) on measures of feasibility (primary aim), burden, acceptability, engagement, and initial pain-related outcomes. Sample size was informed by pilot trial guidelines for RCTs of behavioral interventions,  and past similar studies, that suggest 30 participants per condition is sufficient for determining feasibility and acceptability, and feasibility of a future definitive trial. We anticipate no more than 25% attrition by 1 month post- baseline, based on previous psychosocial studies with cancer patients. Both groups of 30 participants are needed because we aim to demonstrate two types of feasibility: feasibility of the PainPac app, which only requires the 30 PainPac participants, and feasibility of the subsequent larger RCT (i.e., recruitment, assessments), which requires all 60 PainPac and PCST-Video participants. We are recruiting both sexes and all genders, and we expect a nearly equal sample size between sexes. To account for sex as biological variable, we will describe all outcomes disaggregated by sex. We will examine intervention effects and use this data to optimize PainPac. Aim 1. Feasibility (accrual, attrition, adherence), burden, acceptability, and engagement will be assessed post-treatment and descriptive statistics will be produced for PainPac and PCST-Video. Overall trial feasibility benchmarks include reaching target accrual (N=60) within 15 months and <25% attrition by 1 month post- baseline. Descriptive statistics will be used to report non-eligibility and refusal. Data of non-completers will be compared to completers. 75% completed will serve as our feasibility benchmark. If >25% of consented patients drop out, PainPac will not be considered feasible. We do not expect attrition to be greater in the PainPac condition compared to PCST-Video. PainPac feasibility benchmarks include protocol adherence indicated by calculating the degree to which participants are willing/able to complete study assessments (pre, post, follow- up) and the 4 PainPac skills modules or 4 PCST-Video sessions. 75% completed will serve as our benchmark. If >25% of consented patients do not complete the intervention (modules /sessions and assessments), PainPac will not be considered feasible. We expect adherence in the PainPac condition will be at least comparable to PCST-Video. Patient Burden will be measured as a continuous variable by assessing physical, emotional, and financial burden of engaging in the study intervention. We expect burden will not be greater in PainPac compared to PCST-Video. Patient Engagement will be assessed by electronic app data (e.g., PainPac weekly log-ins) and patient self-report defined as the

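### The Aim 2 power statement (>80% for d=0.74 at N=60) assumes no attrition; at the section's own 25% ceiling, unadjusted observed-case power is about 68%

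*Combined protocol and SAP*

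**What the plan says.** All of this is in Data Analysis & Statistical Considerations unless another section is named.

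- **Power.** The Aim 2 text takes the proposed sample size of 60 and says "an a priori power calculation using G-Power suggests we will have" more than 80% power for d=0.74, at a two-sided 5% level.
- **Attrition.** The opening paragraph says "We anticipate no more than 25% attrition by 1 month post- baseline". It also treats 60 as the accrual target, to be reached within 15 months.
- **Basis for N.** The sample size comes from pilot-trial guidelines and similar studies, on the ground that "30 participants per condition is sufficient for determining feasibility and acceptability".
- **Aim 2 analysis.** "Between-group differences at follow-up will be characterized using" Cohen's d with 95% confidence intervals. Pain medication and disease stage or treatment are not adjusted for here: "we will describe these variables and include them, when appropriate, as covariates in future larger trials". No model and no handling of missing Aim 2 outcomes is given.
- **Status of the power figure.** The sentence after it says that "our analytic plan focuses on describing between-group differences rather than testing for significant effects".
- **Timing.** Design & Procedures places post-treatment (A2) four weeks after baseline and then the "1 month follow-up (A3; 1 month post-A2").

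**The concern.** The power sentence uses the number enrolled, while the section around it plans for up to a quarter of participants to be lost. The effect size of 0.74 is almost exactly the smallest that 30 per arm can detect with 80% power, so there is no slack to absorb any loss.

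This sentence is also the plan's only statement of what N=60 can show for Aim 2. A reader, including whoever plans the larger trial, would take from it that the study will have more than 80% power for d=0.74. That is true only with essentially complete outcome data, which the plan itself does not promise. The planned output is an effect size with an interval, yet the expected interval width, which would inform that reader better, is not given.

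**Working it through.** **Inputs from the plan.** d=0.74; two-sided alpha 0.05; 30 per arm; attrition of at most 25% by one month after baseline. At that ceiling, 60 × 0.75 = 45 are analysed, taken as 23 and 22. The case of 50 analysed (25 per arm, about 17% loss) is illustrative. For context, Background & Significance reports 16% attrition in the team's earlier videoconference arm, and 60 × 0.84 = 50.4.

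**Formulas.**
- Power: two-sample t test, noncentral t with df = n1 + n2 − 2 and noncentrality d × √(n1·n2/(n1+n2)).
- Expected 95% CI half-width for d near 0: t(0.975, df) × √(1/n1 + 1/n2).

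**Reproducing the plan's figure.** With 30 per arm the noncentrality is 0.74 × √15 = 2.87 on 58 df, and power is 80.5%. The smallest d with 80% power is 0.736. The stated figure is therefore reproduced, with all 60 analysed.

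**Allowing for loss.** With 23 and 22 analysed, the noncentrality is 0.74 × √(506/45) = 2.48 on 43 df.

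| Analysed | Power at d=0.74 | Smallest d with 80% power | 95% CI half-width, d near 0 |
|---|---|---|---|
| 60 (30/30) | 80.5% | 0.74 | 0.52 |
| 50 (25/25) | 72.7% | 0.81 | 0.57 |
| 45 (23/22) | 67.9% | 0.85 | 0.60 |

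Exactly 80% power needs about 29.7 per arm. Losing one participant (30/29) gives 79.8%.

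**Sensitivity to baseline adjustment.** The plan names no adjusted model, so the baseline–outcome correlation ρ is an assumption. With one baseline covariate the effect becomes d/√(1−ρ²), on n1 + n2 − 3 df. That is 0.74/√0.91 = 0.776 at ρ=0.3 and 0.74/√0.75 = 0.854 at ρ=0.5.

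| Analysed | ρ=0.3 | ρ=0.5 |
|---|---|---|
| 60 | 84.0% | 90.2% |
| 50 | 76.6% | 84.1% |
| 45 | 72.0% | 79.9% |

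**Timing.** The 25% ceiling is set at one month, close to A2. The Aim 2 contrast is at follow-up, the label the plan gives to A3, about two months after baseline. No attrition figure is given for A3, so loss there could be larger. It cannot be quantified from the documents.

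**The case against.** The strongest reply is that nothing stated is false and nothing depends on it. The power figure is tied explicitly to N=60 and is correct for 60. The next sentence says the analysis is descriptive, the sample size rests on feasibility, and no test, go/no-go rule or decision uses the 80%. Power for a test that will not be run has no operational effect, whether it is 80% or 68%. All of this stands, and it is why the point is minor.

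Further, 25% is a ceiling, and loss above it is the plan's own mark of infeasibility, so 68% describes the edge of the planned range and not the expected case. That is also right. But the shortfall starts with the first lost participant, and a loss of about one in six already brings power to about 73%.

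Third, the calculation assumes that each dropout contributes no Aim 2 outcome and that the comparison is unadjusted. Baseline adjustment at ρ=0.5 would bring power with 45 analysed back to about 80%. This is a fair condition on the result. The plan, however, describes no such model, so the unadjusted figure is the one that matches its text.

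Finally, whether follow-up in Aim 2 means A3 is not stated there. The A3 remark is a possibility and adds no weight to the figures above.

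**Conclusion.** The point holds. The calculation is correct for 60 analysed, but the condition of full retention is unstated and conflicts with the attrition anticipated in the same section. Under that section's ceiling, power for d=0.74 is about 68%, not more than 80%, and 80% power needs d of about 0.85. These values assume an unadjusted two-sample comparison of observed cases, with every dropout missing the Aim 2 outcome. With baseline adjustment and an assumed correlation of 0.3 to 0.5, power with 45 analysed would be about 72% to 80%.

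The practical effect is small. Expected precision for d widens from about ±0.52 to about ±0.60. The primary feasibility aim, N and the planned analysis are unaffected.

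**What to change.** Replace the power sentence in the Aim 2 text with wording such as:

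> With 60 randomised, power for d=0.74 (two-sided 0.05, unadjusted comparison of observed cases) is 80% if all 60 are analysed, about 73% with 50 and about 68% with 45 (25% attrition; 80% power for d of about 0.85). The expected 95% CI half-width for d near 0 is about 0.52 with 60 and 0.60 with 45.

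Alternatively, delete the power sentence and give only the expected half-widths, which suit the descriptive plan better. If a baseline-adjusted comparison is intended, say so and state the assumed baseline–outcome correlation next to the figures.

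The cost is one sentence rewritten or removed, and a less favourable stated power. No extra patients are needed.
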